6.2. SERIOUS ADVERSE EVENTS (SAES)

An AE shall be classified as serious if it:

- Results in death.
- Is life-threatening.

Life threatening in the definition of serious refers to an event in which the participant was at risk of death at the time of the event, it does not refer to an event which hypothetically might have caused death if it were more severe.

- Requires in-patient hospitalisation or prolongation of existing hospitalisation.

Hospitalisation is defined as in-patient admission or care regardless of duration.

Out-patient treatment in an emergency room is not in itself an SAE, although the reasons for it may be (e.g. bronchospasm, laryngeal oedema). Elective surgery, hospitalisation for social reasons (with no causal AE), or hospital admissions and/or surgical operations planned before or during this study are not considered AEs if the illness or disease existed before the participant was enrolled in the study, provided that it did not deteriorate in an unexpected way during the study.

- Results in persistent or significant disability/incapacity.
- Is a congenital anomaly/birth defect.
- Is an important medical event.

This includes events that may not be immediately life-threatening or result in death or hospitalisation but may jeopardise the participant or may require intervention to prevent one of the other outcomes listed above.

6.3. RECORDING OF ADVERSE EVENTS

CONFIDENTIAL

Page 16 of 21

Cardiology Department, HNELHD
Clinical Trial Protocol: PRESSURE-AF

Version: 1.4
Date: 24/11/2020

AEs will be captured from the time of informed consent until the discharge. Participants will be asked whether they have experienced any AEs. If a participant has concern over ongoing symptoms or events, they are encouraged to see their local GP or the emergency department to address these concerns.

It is preferable that AEs are reported as diagnoses if one is able to be made, rather than individual signs and symptoms. The AE description, start and stop dates, intensity, causality and outcome must be recorded, as well as any actions taken.

Unless a diagnosis is made, or signs and symptoms are present, laboratory values or vital signs abnormalities should only be reported as AEs if they cause the participant to discontinue from the trial, the investigator feels it is clinically significant, or they meet a criterion for a SAE.

6.4. REPORTING OF SERIOUS ADVERSE EVENTS

Follow-up information on SAEs must be reported by the investigational site within 24 hours. If a non-serious AE becomes serious, this and other relevant follow-up information must also be provided within 24 hours.

All SAEs will be recorded in the participant records and the CRF.

The investigator must notify their Independent Ethics Committee (IEC) of any SAEs occurring at their site, within the time specified by the IEC.

6.5. FOLLOW-UP OF ADVERSE EVENTS AND SERIOUS ADVERSE EVENTS

All AEs and all SAEs must be followed by the Investigator until resolution, until the AE stabilises or is recognised as a permanent condition by the Investigator, or until the participant is lost to follow up, whichever comes first. Follow-up investigations may be necessary according to the Investigator's medical judgement.

7. DATA MANAGEMENT

Data collection and entry into the CRF will be completed by authorised study site personnel designated by the Investigator. Appropriate training and security measures will be completed with the Investigator and all authorised study site personnel prior to the study being initiated and any data being entered into the system for any study participants.

All data must be entered in English. The CRFs should always reflect the latest observations on the participants in the trial; therefore, the CRFs are to be completed as soon as possible after the participant's visit. The Investigator must verify that all data entries in the CRFs are accurate and correct. If some assessments are not done, or if certain information is not available or not applicable or unknown, this should be indicated in the CRF. The Investigator will be required to sign off on the clinical data.

8. STATISTICAL ANALYSIS

8.1. INTERIM ANALYSIS

After 12 months of patient enrolment, the statistical team will review recruitment and adverse events. 30% recruitment of the total sample size (308) will be required after 12 months in order to continue the trial. If a significant difference in adverse events is detected, the appropriateness of ongoing recruitment will be discussed with the local research ethics committee. Primary and secondary efficacy outcomes will not be assessed at this time to reduce the potential for bias.

Cardiology Department, HNELHD
Clinical Trial Protocol: PRESSURE-AF

Version: 1.4
Date: 24/11/2020

8.2. STATICAL ANALYSIS PLAN

Continuous variables will be reported as mean \pm standard deviation or as median and percentiles if appropriate. Normally distributed variables will be compared using the paired Student's t-test. Otherwise comparisons between both the groups will be performed using the Mann–Whitney U test. Categorical variables will be stated as absolute and relative frequencies and compared using the χ^2 test. All tests are two-tailed. A P-value of <0.05 will be considered as statistically significant.

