Number of participants:	
It is planned that 308 participants will be randomised in a 1:1 ratio to one of two treatment arms:
 
• 154 will undergo standard direct current cardioversion.
➤ 1 shock – 150 Joules without chest pressure➤ 1 shock – 200 Joules without chest pressure➤ 1 shock – 360 joules without chest pressure➤ 1 shock – 360 joules with chest pressure• 154 will undergo an initial strategy of chest pressure.
➤ 1 shock – 150 Joules with chest pressure➤ 1 shock – 200 Joules with chest pressure➤ 1 shock – 360 Joules with chest pressure➤ 1 shock – 360 joules with chest pressure
Key inclusion	Participants who:

CONFIDENTIAL

Cardiology Department, HNELHD
Clinical Trial Protocol: PRESSURE-AF

Version: 1.4
Date: 24/11/2020

- criteria:
- Aged over 18 years of age.
 - Have Atrial Fibrillation.
 - Are referred for direct current cardioversion for atrial fibrillation.
 - Three weeks of therapeutic anti-coagulation prior to cardioversion or transoesophageal echocardiography excluding left atrial appendage thrombus.
- Key exclusion criteria:
- Participants with:
- Pregnant or breastfeeding females.
 - Inability to provide informed consent.
 - Other atrial tachyarrhythmias (atrial flutter or multifocal atrial tachycardia)
 - Medical comorbidity where anticoagulation is contra-indicated
- Test strategy:
- Direct current cardioversion for atrial fibrillation with and without chest pressure as the initial strategy.
- Duration of study per participant:
- Day of procedure only.
- Criteria for evaluation:
- Primary efficacy endpoints
- Total joules provided during encounter.
- Secondary efficacy endpoints:
- Success of first shock for reversion to sinus rhythm.
 - Transthoracic impedance at the time of shock.
 - Sinus rhythm at post cardioversion ECG
- Safety and Tolerability Endpoints
- Patient chest pain post cardioversion (Ordinal Scale 0-10).
 - Incidence of shock provided to proceduralist.
- Statistical methods and analyses:
- Analysis Sets
- Full analysis set (FAS) Intention to Treat (ITT) Protocol: All participants randomised into the study. Participants will be analysed according to the intervention to which they were randomised. Efficacy analyses performed in the FAS are considered supportive of analyses performed in the PP set.

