 - Per-protocol (PP) set: All participants from the ITT population who completed the study in compliance with the protocol and who reported no major violation of the study protocol. Participants will be analysed according to the intervention which they received. The final decision to exclude a participant from the PP set will be taken during a blinded data

CONFIDENTIAL

review meeting before database lock. Efficacy analyses performed in the PP set are considered supportive of analyses performed in the ITT set.

Sample Size

A retrospective review of 12 months of direct current cardioversions was performed at our centre. The mean energy provided during an encounter was 280 ± 188 Joules. Assuming a mean reduction of 60 joules in energy in the intervention group (one third of the standard deviation), a total of 308 patients (154 in each arm) would need to be recruited for an alpha of 0.05 and power of 0.8. This has been discussed and confirmed with statisticians at the Hunter Medical Research Institute.

Statistical Analyses

Continuous variables will be reported as mean \pm standard deviation or as median and percentiles if appropriate. Normally distributed variables will be compared using the paired Student's t-test. Otherwise comparisons between both the groups will be performed using the Mann-Whitney U test. Categorical variables will be stated as absolute and relative frequencies and compared using the χ^2 test. All tests are two-tailed. A P-value of <0.05 will be considered as statistically significant.

Sensitivity analyses of the primary endpoint will be performed in the FAS to assess the impact of missing data on the robustness of the primary analysis. The primary analysis will also be repeated in the PP set.

The following secondary endpoints will be analysed and summarised using the methods described for the primary endpoint:

- Success of first shock for reversion to sinus rhythm.
- Average transthoracic impedance.
- Chest pain post procedure – ordinal 0-10 scale.
- Shock provided to the provider.

Successful cardioversion is defined as sinus rhythm 1 minute after cardioversion.

Cardiology Department, HNELHD
Clinical Trial Protocol: PRESSURE-AF

Version: 1.4
Date: 24/11/2020

Table of Contents

PROTOCOL SYNOPSIS	2
LIST OF ACRONYMS AND ABBREVIATIONS	8
1. BACKGROUND AND RATIONALE	11
1.1. ATRIAL FIBRILLATION AND DIRECT CURRENT CARIOVERSION	11
1.2. CLINICAL STUDIES OF DIRECT CURRENT CARIOVERSION FOR ATRIAL FIBRILLATION.....	11

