2.3. OVERALL TRIAL DESIGN

This is a multi-centre, randomised controlled study to assess the efficacy, and safety of direct current cardioversion for atrial fibrillation. Participants will be screened on the day of direct current cardioversion. Consenting participants will be randomised 1:1 to have an initial strategy of chest pressure with cardioversion or an initial cardioversion without chest pressure.

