2.5. STUDY PERIOD/DURATION OF PARTICIPANT PARTICIPATION

The duration of the study for each participant is the day of the procedure.

It is anticipated that recruitment will take approximately 24 months. The study period is expected to be 2021-2023.

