2.7.5. Method of assigning participants to treatment group

Participant eligibility will be established before randomisation. Eligible participants who consent to involvement will be assigned to either the control or intervention arm in a 1:1 ratio. Patients will be

Cardiology Department, HNELHD
Clinical Trial Protocol: PRESSURE-AF

Version: 1.4
Date: 24/11/2020

randomised via a randomisation app. This app, given to all researchers, will provide synchronised information about patient allocations.

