4. TRIAL ENDPOINTS

4.1. EFFICACY ENDPOINTS

4.1.1. Primary

- Total joules provided to patient.

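### The t-test named for normally distributed variables is the paired one, although the trial compares two independent randomised arms that contain no pairs.

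*Protocol*

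**What the plan says.** **The test.** Section 8.2 of the protocol, and the Statistical Analyses part of the synopsis, give the same rule for continuous variables: "Normally distributed variables will be compared using the paired Student's t-test". The next sentence covers everything else: "Otherwise comparisons between both the groups will be performed using the Mann–Whitney U test". No separate test is named for the primary endpoint. The synopsis treats this rule as the primary-endpoint method and extends it to the secondary endpoints, among them average transthoracic impedance.

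**The design.** Section 2.3: "Consenting participants will be randomised 1:1 to have an initial strategy of chest pressure with cardioversion or an initial cardioversion without chest pressure". Section 2.7.5 says that participants are "assigned to either the control or intervention arm in a 1:1 ratio". The synopsis: "It is planned that 308 participants will be randomised in a 1:1 ratio to one of two treatment arms". Section 2.5: "The duration of the study for each participant is the day of the procedure". The primary endpoint in section 4.1.1 is one figure per person: "Total joules provided to patient".

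**The analysis set.** Section 8.3 puts every randomised participant in the full analysis set and analyses primary and secondary outcomes on that set.

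**The concern.** A paired t-test works on within-pair differences, so it needs a reason why one observation belongs with one particular other observation. Nothing in the protocol supplies that for the efficacy comparison. There is no matching, no second period and no before-and-after contrast between arms. The pressure used for a fourth shock in the control arm is a step within that arm's strategy and does not create a pair.

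An analyst who followed the text literally for a variable judged normal would have to make up a pairing, for instance by enrolment order. Two things then go wrong:

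- The p-value becomes a property of the file order as well as of the data, so the pre-specified analysis no longer gives one answer per data set.
- If the arms differ in size, through allocation or missing values, the surplus patients have no partner and fall out. That conflicts with the full analysis set in section 8.3.

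**Working it through.** **1. Which test does the sample size assume?** Inputs from the synopsis: "The mean energy provided during an encounter was 280 ± 188 Joules", a reduction of 60 J, alpha 0.05, power 0.8, and two-tailed tests.

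Independent two-sample formula: n per arm = 2 × [SD × (z₀.₉₇₅ + z₀.₈₀) / difference]² = 2 × [188 × (1.960 + 0.842) / 60]² = 154.1. This matches the stated 154 per arm (308 in total). At 154 per arm, power is 0.800 by the normal approximation and 0.797 by the exact t calculation.

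Paired calculations (t-based), for comparison:

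| Assumption | Pairs needed |
|---|---|
| 188 J is the SD of the differences (same as within-pair correlation 0.5) | 79 |
| 188 J is the SD of one measurement, correlation 0.3 | 110 |
| 188 J is the SD of one measurement, correlation 0 | 156 |

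The last row comes close to 154 only because zero correlation is the independent case. The sample size takes no credit for pairing.

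**2. What does an invented pairing do to the p-value?** With equal SDs and n = 154 per arm, the paired standard error is 188 × √[2(1 − r)/154], where r is the correlation that the row order happens to create. The unpaired standard error is the r = 0 case: 188 × √(2/154) = 21.42 J. The mean difference is the same either way, so only r moves the result.

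The check used simulated normal data, scaled to SD 188 J in each arm, with 10,000 random re-orderings of one arm:

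| Observed difference | Unpaired p | Paired p, range over orders | Central 95% |
|---|---|---|---|
| 42.5 J (t = 42.5/21.42 = 1.98) | 0.048 | 0.020 to 0.086 | 0.032 to 0.067 |
| 60 J (t = 60/21.42 = 2.80) | 0.005 | 0.001 to 0.015 | 0.003 to 0.010 |

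At 42.5 J, 54% of the orders fell below 0.05. Sorting both arms in the same direction gave p < 1e-40, and sorting them in opposite directions gave p = 0.16. At 60 J, every random order stayed below 0.05.

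**3. Average error rates.** With purely random pairing, 20,000 simulated trials gave a type I error of 5.0% and a power of 79%.

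**4. Unequal arms.** Section 2.7.5 mentions a randomisation app but not the method. If allocation were simple, the chance of exactly 154/154 is C(308,154)/2³⁰⁸ = 4.5%, and the mean imbalance is about √(2 × 308/π) = 14 patients. Blocking would make the imbalance much smaller, although missing values could still leave unequal numbers.

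**5. Would total joules reach the paired branch?** Under the shock sequences in sections 2.7.1 and 2.7.2, cumulative energy can only be 150, 150 + 200 = 350, 350 + 360 = 710 or 710 + 360 = 1070 J. Section 1.2.2 reports first-shock and last-shock success of 71% and 87% at the centre. The intermediate rates are not given and were assumed:

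| Assumed cumulative success after shocks 1, 2, 3 | Skewness |
|---|---|
| 71%, 76%, 81% | 1.28 |
| 71%, 79%, 83% | 1.45 |
| 71%, 80%, 85% | 1.54 |
| 71%, 85%, 87% | 1.86 |

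In 1,000 samples of 154 from each of these, the Shapiro-Wilk test rejected normality every time (largest p below 1e-16). The assumed distributions have SDs of 311 to 365 J, against 188 J in the retrospective review, so they illustrate shape only.

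**The case against.** The strongest reply is that this is a slip with little reach. The paired test is only one branch of a conditional rule. The other branch, in the next sentence, is a valid test for independent groups and speaks of comparing the two groups, and the sample size assumes independent groups as well. A four-valued, skewed total would very probably be judged non-normal, so the primary endpoint would go to Mann-Whitney. First-shock success, sinus rhythm on the post-procedure ECG and shock to the proceduralist are binary and go to the chi-squared test. Pain is a 0-10 ordinal score. That leaves impedance as the plausible candidate. Type I error under random pairing is not inflated, and the marked swings in p occur near the 0.05 threshold.

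Most of this stands, and it rules out two stronger readings. A reader might infer that the paired t-test is the primary analysis and that the primary result would therefore be invalid. The text does not say so, because the test applies only to variables judged normal. A reader might also infer an inflated false-positive rate, which the calculation does not show.

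The reply does not remove the fault. The sentence appears twice and nothing in the protocol corrects it. It still governs any variable judged normal, and it would govern total joules if an analyst treated that variable as normal. That is conceivable, since the trial is powered on a difference in means.

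**Conclusion.** The point holds as an error in one branch of the stated analysis rule. For a variable judged normal, the named test does not fit two independent arms. It yields a p-value that depends on an arbitrary and manipulable pairing (0.020 to 0.086 around an unpaired 0.048 in the example), and it cannot keep all randomised patients when arm sizes differ. It also disagrees with the plan's own fallback test and sample-size calculation.

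The effect on the primary p-value may be small, because total joules would probably be analysed by Mann-Whitney. That expectation rests on the protocol's shock sequence being followed and on assumed intermediate success rates. The example p-values rest on simulated normal data with SD 188 J. The figure of about 14 unmatched patients holds only under simple randomisation, which the protocol does not state.

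**What to change.** In the synopsis (Statistical Analyses) and in section 8.2, replace the paired test with an *independent-samples (unpaired) t-test*. Welch's unequal-variance version is a reasonable choice, but the essential correction is the move from paired to unpaired. The Mann-Whitney and chi-squared wording can stay as far as this point is concerned.

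The cost is one change of wording in two places. The sample size stays at 308, with power of 0.797 to 0.800 at 154 per arm, and no data collection or trial procedure is affected.

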8.3. ANALYSIS SETS

The following sets will be used for the statistical analyses:

Intention to treat full analysis set (ITT FAS): All participants randomised into the study will be included in the ITT FAS. Participants will be analysed according to the intervention to which they were randomised. Primary and secondary outcomes will be analysed based on the FAS.

Per-protocol (PP) set: All participants from the ITT FAS population who completed the study in compliance with the protocol. Participants will be analysed according to the intervention which they received. The final decision to exclude a participant from the PP set will be taken during a blinded data review meeting before database lock. Efficacy analyses performed in the PP set are considered supportive of analyses performed in the ITT set.

8.4. PRE-SPECIFIED POST-HOC ANALYSIS

Post-hoc analyses will be performed based on the following variables:

- Body Mass Index (greater and less than 30 ,40 and 50)
- Left Atrial Size (indexed left atrial size/volume)
- Age (younger and older than 40, 60, and 80 years of age)
- Anti-arrhythmic therapy (Beta Blockers, Sotalol, Flecainide and Amiodarone)

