8.5. DATA ANALYSIS CONSIDERATIONS

All efficacy and safety data will be listed and summarised using descriptive statistics by treatment group. The descriptive summary for the categorical variables will include counts and percentages. The descriptive summary for the continuous variables will include means, medians, standard deviation and minimum and maximum values. Where possible, data from participants who withdraw prematurely from the study will be included in any analysis.

All statements of statistical significance will be based on a two-sided test at the 5% level of significance, unless stated otherwise. If the study is prematurely discontinued, all available data will be listed and a review will be carried out to determine which statistical analyses are considered appropriate.

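### Section 8.4 calls planned subgroups both pre-specified and post-hoc, and cuts BMI and age at three points each under an unqualified 5% rule; one continuous interaction per variable would be better

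*Protocol*

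**What the plan says.** Section 8.4 of the protocol is headed "PRE-SPECIFIED POST-HOC ANALYSIS" and opens with "Post-hoc analyses will be performed based on the following variables". Its four bullets are:

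- "Body Mass Index (greater and less than 30 ,40 and 50"
- "Left Atrial Size (indexed left atrial size/volume", with no cut-point
- "Age (younger and older than 40, 60, and 80 years of age"
- "Anti-arrhythmic therapy (Beta Blockers, Sotalol, Flecainide and Amiodarone"

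Section 8.2 names a t-test, the Mann-Whitney test and the chi-squared test, and adds: "A P-value of <0.05 will be considered as statistically significant". Section 8.5 extends this: "All statements of statistical significance will be based on a two-sided test at the 5% level of significance, unless stated otherwise". Section 8.4 states nothing otherwise. The sample size paragraph in the synopsis sizes the trial for the overall comparison of total energy only.

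**The concern.** Three features of the text combine badly.

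- **The label contradicts itself.** Subgroups listed before recruitment are planned. The two words carry different evidential weight, and this heading would support either description when results are reported.
- **The cut-points are poorly fixed.** Three cuts on one continuous variable can mean three overlapping two-way splits or four bands, and the text does not say which. Either way, a continuous variable is reduced to categories.
- **The 5% rule has no exception.** Any subgroup p-value below 0.05 may be called significant.

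At stake is a false claim that chest pressure works better in some patients. BMI is the likely candidate, because section 1.3 rests the rationale on lower transthoracic resistance. In a trial sized only for the main effect, a uniform benefit can reach significance in one stratum and miss it in another simply because the strata differ in size.

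**Working it through.** **Inputs from the protocol.** 308 patients, 154 per arm; SD 188 J; effect 60 J; two-sided 5%; power 0.80 (synopsis, Sample Size). Cut-points and drugs from section 8.4; significance rule from sections 8.2 and 8.5.

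**Inputs assumed, because the documents give none.** BMI normal with mean 31 to 33 and SD 6 to 7; age normal with mean 65 to 66 and SD 11 to 12; drug use 50%, 20%, 15% and 20%; one split for left atrial size.

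**1. The plan's own figure.** n per arm = 2 × (1.960 + 0.8416)² × 188² / 60² = 2 × 7.849 × 9.818 = 154.1, against the stated 154. Power at 154 per arm is 0.80. The design figure reproduces.

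**2. Number of splits if each is tested separately.** 3 (BMI) + 3 (age) + 1 (left atrium) + 4 (drugs) = 11.

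**3. Chance of at least one false positive when there is no effect anywhere.** For k independent tests this is 1 − 0.95^k. Nested cut-points are correlated, so trials of 308 patients were also simulated with a normal outcome (6,000 replicates for interaction tests, 2,000 for within-stratum tests). Cells too small to test counted as not significant.

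| Tests | Independent | Simulated |
|---|---|---|
| 6 BMI and age interactions | 1 − 0.95^6 = 26.5% | 19–21% |
| 11 interactions | 1 − 0.95^11 = 43.1% | about 38% |
| 22 within-stratum tests | 1 − 0.95^22 = 67.6% | about 44% |

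**4. Power, from the plan's own figures.** For an interaction, SE = 188 × √(4/n₁ + 4/n₂), where n₁ and n₂ are the two stratum sizes.

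- Even split: 188 × √(8/154) = 42.8 J. A difference between strata as large as the whole 60 J effect then has 29% power.
- 20/80 split: 20% power. 10/90 split: 13% power.
- A true 60 J effect inside one stratum has 51% power at half the sample and 14% at one tenth.

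**5. Information kept by a cut.** For a normal covariate and a linear interaction, the share kept is φ(z)² / [P(1 − P)], where z is the standardised cut-point, φ(z) the normal density there and P the proportion below the cut.

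| Cut | Share kept |
|---|---|
| BMI 30 or age 60 | 58–63% |
| BMI 40 | 27–44% |
| Age 80 | 31–38% |
| Age 40 | 8–10% |
| BMI 50 | 1–6% |

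**6. Size of the extreme strata under the same assumptions.** About 0 to 2 patients with BMI over 50, and 4 to 5 aged under 40.

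**7. With one interaction per listed variable.** Four tests, if p-values were used at all: 1 − 0.95^4 = 18.5% when independent.

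**The case against.** The best defence is that section 8.4 fixes very little. It names no test, and 8.5 governs statements of significance that are made without requiring any for subgroups. The SAP is not shown and may supply an interaction test, a multiplicity rule or exploratory status. Calling an analysis post-hoc usually weakens a claim, so the heading may simply mean secondary looks listed in advance. Left atrial size may be intended as continuous, the drugs as one factor, and the cut-points as bands. That would be four tests and 18.5%, not 11. Linear modelling brings an assumption of its own.

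Most of this stands, and it rules out several stronger readings that a reader might infer:

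- **That the protocol prescribes significance tests within each stratum.** It does not. This is only what the named two-group tests would lead to if nothing else is added.
- **That there are at least 11 splits.** Eleven is one reading, not a minimum.
- **That the error rate is 68%.** That figure treats 22 overlapping strata of the same patients as independent; allowing for the overlap gives about 44%.
- **That the extreme strata will be nearly empty.** They may be, but the documents give no BMI or age distribution.
- **That the sponsor intends confirmatory subgroup claims.** Nothing in the text shows this.

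The defence does not remove the contradictory heading, the ambiguous cut-points, or the 5% rule that makes no exception for 8.4. Those are in the text whatever the SAP adds.

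**Conclusion.** The point holds as a cheap improvement to a stated rule. Section 8.4 needs a consistent label and a better use of BMI and age than three cuts each. If every cut-point and drug is tested separately at 5%, there is roughly a two-in-five chance of at least one spurious subgroup finding when there is no effect anywhere. Power to detect real effect modification is low to begin with, and categorising lowers it further.

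The false-positive figures depend on the 11-split reading, and the simulated ones also on the assumed covariate distributions. The information-loss and stratum-size figures are illustrative for the same reason. The interaction and subgroup power figures rest only on the protocol's SD, effect and sample size, for the stratum shares shown. The primary endpoint, its analysis and the sample size are not affected.

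**What to change.** Rename section 8.4 'Pre-specified exploratory subgroup analyses' and replace the split-by-split approach:

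- For total joules, fit a linear regression with treatment, the covariate and their interaction, one model per listed variable.
- Keep BMI, age and indexed left atrial size continuous. Enter the drug therapies together and test their interactions with treatment jointly.
- Report interaction estimates in joules with 95% confidence intervals. State that 8.4 is exempt from the 5% rule in sections 8.2 and 8.5, so that the joint drug test is descriptive too.
- Keep the cut-points for descriptive display only, and say whether they define bands or two-way splits.

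The protocol currently contains no regression model, so this adds a short paragraph, a little modelling and a linearity assumption to check. Trial conduct, sample size and the primary analysis do not change.
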